#### **Week 16 (FSV) (+/- 2 weeks)/ Follow-up:**

Once the patient's ulcer has completely healed or the 16 weeks of treatment ends, the patient will return for their final study visit.

- If complete healing is achieved in less than 16 weeks, a follow-up visit will be scheduled at 16 weeks after enrollment.
  - Patients will be instructed to contact the study Physician should the ulcer recur.
  - The initially assigned oxygen treatments will be stopped at this time.
- Digital imaging of the ulcer to measure the response to therapy
- Quality of life questionnaire (SF-36) will be administered to all patients at 16 weeks.
- If the wound has not healed in 16 weeks, the wound is assessed as to its recent response to treatment.
  - Wounds, which have decreased less than 10% in wound surface area during the preceding 4 weeks, are designated as "Quiescent". Quiescent wounds are considered to be non-responders.

#### **STUDY ASSESSMENTS AND PROCEDURES**

- a. **Wound Healing rates.** Wound healing rates will be determined from wound area measurement at baseline vs final visit using wound photography and Wound Matrix. Wound Matrix will be used to capture wound image, instantly upload wound images and obtain measurement of wound area data elements at the point of care. Measurement should be performed after debridement if there is one as a part of SoC. Wound matrix is a digital wound measurement

system that utilizes tablet/smartphone camera for taking a digital image of the wound in presence of a standard Ruler for size calibration. The image is automatically tracked and measured. The software tracks the outer perimeters of the wounds using a proprietary algorithm.

**b. Quality of life assessment**

SF-36- All patients will be administered the Medical Outcomes Study Short Form (SF-36) at baseline and end of study. The SF-36 is an indicator of the overall health status

**c. Wound complications such as wound infection.** The following standard scale for wound infection will be used:

Infection Level:

- **Level 0** - Uninfected or no signs of infection
- **Level 1 – Mild** Infection present with presence of any two of the following items:
  - Local swelling or induration
  - Erythema >0.5 to <=2 cm around the ulcer
  - Local tenderness or pain
  - Local warmth
  - Purulent discharge (thick, opaque to white, or sanguineous secretion)
  - Local infection involving only the skin and the subcutaneous tissue (without involvement of deeper tissues and without systemic signs as described below).
  - Exclude other causes of an inflammatory response of the skin (e.g., trauma, gout, acute Charcot neuro-osteoarthropathy, fracture, thrombosis, venous stasis)
- **Level 2 – Moderate** Local infection (as described above) with presence of erythema >2 cm, or involving structures deeper than skin and subcutaneous tissues (e.g., abscess, osteomyelitis, septic arthritis, fasciitis), and no systemic inflammatory response signs (as described below)
- **Level 3 – Severe** Local infection (as described above) with presence of the signs of SIRS, as manifested by two or more of the following:
  - Temperature >38 or <36C
  - Heart rate >90 beats/min
  - Respiratory rate >20 breaths/min or PaCO2 <32 mm Hg
  - White blood cell count >12,000 or <4000 cu/mm or 10% immature (band) forms

**d. Cost of care.** Cost will be calculated including SOC expenses such as patient-of-pocket expenses and expenses billed to the insurance company, as well as theoretical costs associated with topical oxygen therapy. These

costs will be analyzed through the Comprehensive Wound Center Standard of Care billing. Due to the cost analysis portion of the study, this study will be limited to Medicaid/ Medicare and dual eligible recipients only.

### **Compliance:**

The results of wound care are highly dependent upon compliance with specified treatment regimens. To ensure optimum subject compliance, research staff will counsel subjects at each study visit and assist to facilitate the delivery of appropriate care. Subjects will be encouraged to maintain scheduled appointments and comply with appropriate wound care (TO+SoC or SOC). Study subjects will be asked to record their wound care treatment by using a patient diary between visits. These diaries will be collected at each visit and reviewed for compliance. For the purposes of this study, subjects meeting either of the following criteria will be considered to be major protocol violators:

1. Subject fails to receive wound treatment for 8 consecutive sessions for any reason
2. Any subject who misses more than 30% of scheduled treatments in a month

Any subject assigned to Topical Oxygen Therapy and meeting criteria for major protocol violators in any two months will be discontinued for the duration of the study. Any study subject who is determined to be noncompliant with their care per the discretion of the principal investigator can be removed from the study.

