**Table-1: Study Timeline**

Week(s)	0 (Visit 1)	1-3	4 (Visit 2) (+/-2 weeks)	5-7	8 (Visit 3) (+/-2 weeks)	9-11	12 (Visit 4) (+/-2 weeks)	13-15	16 (Visit 5) (+/-2 weeks)
Study Visit	✓		✓		✓		✓		✓
Digital Imaging	✓		✓		✓		✓		✓
Topical oxygen or SoC treatment administered at home	✓	✓	✓	✓	✓	✓	✓	✓	✓

**Study Population:** 40 chronic wound patients with diabetes will be recruited based on study inclusion and exclusion criteria by the research personnel. Patients will be randomized into one of the 2 patient groups: the topical oxygen group and the other half randomized into the comparison group.

A proportionate stratified random permuted block design will be used to generate random assignments to the two groups. The stratification will be based on the proportion of patients expected to be seen at a wound center with Wagner grade 1, 2, or 3. This method will ensure balance across the groups and strata and will also account for the difference in the severity over the course of the study period. The biostatistician at the Center for Outcomes Research in Surgery will prepare the master randomization assignment list. The clinical research coordinator will administer randomization using REDCap.

**Blinding.** This is an open label trial. To reduce bias, the personnel involved in evaluating study outcomes will be blinded to treatment group. The standard of care will be provided by their providers at CWC as part of their routine wound care and will not be blinded to treatment group.

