## Statistical analysis.

Univariate analysis will be done using frequencies, mean (SD), median (IQR) to describe the patient cohort. Cumulative incidence of wound healing rates 16 weeks post treatment with 95% confidence interval around the risk estimate will be computed for the two groups (SoC and TO+SoC). Bivariate logistic regression will be used to report the odds of wound healing among those with TO+SoC compared to SoC only. Bivariate analysis to compare secondary outcomes between the groups will be done using Chi-square or Fisher's exact tests for categorical variables and t-tests or Mann-Whitney tests for continuous variables (e.g. QoL ratings from SF-36, costs).

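### Noncompliant subjects in either arm can be removed from the study, and no analysis set or missing-outcome rule says how they count, so the healing rates meant to size the next trial can be biased

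*Combined protocol and SAP*

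**What the plan says.** The Compliance section contains two separate rules.

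- **Both arms, at discretion:** "Any study subject who is determined to be noncompliant with their care per the discretion of the principal investigator can be removed from the study". The missed-session criteria listed just above it define major protocol violators; they do not limit this sentence.
- **Oxygen arm only:** subjects "meeting criteria for major protocol violators in any two months will be discontinued for the duration of the study". The text does not say whether this ends oxygen alone or follow-up as well.

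The section opens with "The results of wound care are highly dependent upon compliance with specified treatment regimens". Compliance is tracked by diary in both arms (At Home Treatments; SoC group only). Under Blinding, "This is an open label trial"; only the personnel who evaluate outcomes are blinded.

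On the outcome, Study Assessments and Procedures states: "Wound healing rates will be determined from wound area measurement at baseline vs final visit using wound photography and Wound Matrix". The Week 16 section ties that visit to healing or the end of treatment: "Once the patient's ulcer has completely healed or the 16 weeks of treatment ends, the patient will return for their final study visit". It schedules a week-16 visit for patients who heal early and has no matching line for patients who were removed.

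On analysis: "Cumulative incidence of wound healing rates 16 weeks post treatment with 95% confidence interval around the risk estimate will be computed for the two groups", followed by a logistic regression for the odds of healing. No analysis set, denominator or missing-outcome rule is given there or elsewhere.

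Some text points the other way. Table 1 schedules week 16 without exception, the Quality of life section says "All patients will be administered the Medical Outcomes Study Short Form (SF-36) at baseline and end of study", and the analysis section excludes nobody.

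**The concern.** Removal happens after randomisation, on the judgement of someone who is not described as blinded, and on a factor that the protocol itself links to healing. If a removed patient has no final visit, there is no healing outcome to analyse. Logistic regression by default drops records with a missing outcome, so the plan's silence probably means a complete-case analysis. Losses could also differ by arm, since only the oxygen arm has the home regimen of four treatment days a week.

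The Objective section says the data are for calculating the sample size of a larger trial. Losing mainly oxygen-arm non-healers makes that trial too small; losing mainly healers makes it too large. The sample size section says that detecting a difference is not the main aim, so what is at stake is the estimates and not a p-value.

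**Working it through.** **Inputs from the plan (Sample size):** 20 per arm; success 50% (oxygen plus SoC) vs 10% (SoC); one-sided Fisher's exact test at 0.05; power at least 80%. **Assumed:** the number of patients lost and their healing status, since the documents give no removal rate.

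**1. The plan's own figure.** Summing over two binomials (20 and 20) all tables with one-sided Fisher p ≤ 0.05 gives power of 83.7%. The stated figure reproduces and is not in dispute.

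**2. Size of a next trial from given rates.** Two-sided 5%, 80% power, normal approximation, with p̄ = (p₁+p₂)/2:

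n per arm = [1.96·√(2p̄(1−p̄)) + 0.8416·√(p₁(1−p₁)+p₂(1−p₂))]² / (p₁−p₂)²

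For 0.50 vs 0.10, p̄ = 0.30: (1.96×0.6481 + 0.8416×0.5831)² / 0.16 = (1.2702 + 0.4907)² / 0.16 = 19.4, so 20 per arm. The smallest n with exact two-sided Fisher power of at least 80% is 23.

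**3. Complete-case rates after assumed losses**, starting from 10/20 vs 2/20:

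| Patients lost | Oxygen | SoC | n per arm (exact Fisher) |
|---|---|---|---|
| none | 10/20 = 50% | 2/20 = 10% | 20 (23) |
| 2 non-healers in each arm | 10/18 = 55.6% | 2/18 = 11.1% | 17 (20) |
| 4 non-healers in each arm | 10/16 = 62.5% | 2/16 = 12.5% | 14 (17) |
| 2 oxygen non-healers only | 10/18 = 55.6% | 10% | 16 (19) |
| 4 oxygen non-healers only | 10/16 = 62.5% | 10% | 12 (16) |
| 4 oxygen only, 2 healed | 8/16 = 50% | 10% | 20 (23) |
| 4 oxygen only, 3 healed | 7/16 = 43.8% | 10% | 26 (30) |
| 4 oxygen only, all healed | 6/16 = 37.5% | 10% | 37 (41) |

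The odds ratio moves too. It is (10/10)/(2/18) = 9.0 with no loss, (10/6)/(2/18) = 15.0 after losing 4 oxygen non-healers, and (6/10)/(2/18) = 5.4 after losing 4 oxygen healers.

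**4. Cost of undersizing.** If the true rates are 50% vs 10%, a next trial of 16 or 12 per arm has power of 71% or 58%, against 81% at 20 (normal approximation). The exact Fisher sizes of 19 and 16 also give 71% and 58%.

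**5. Sampling error for comparison.** The exact 95% interval for 10/20 is 27.2% to 72.8%. With SoC held at 10%, the formula in step 2 gives 80 per arm at the lower limit and 9 at the upper.

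**The case against.** The strongest case against has four parts.

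- **Sampling error is larger than the bias shown.** The interval for 10/20 alone sizes a next trial anywhere from 9 to 80 per arm, which contains the whole 12 to 37 range. This is true, and it limits practical impact. But the reported confidence interval shows sampling error, and it does not show selective loss.
- **The 12 to 37 range comes from one-arm losses.** The discretionary rule applies to both arms, and the oxygen-only rule most naturally ends oxygen and not follow-up (the Adverse events section speaks of discontinuing treatment). On that reading the oxygen-only rule loses no outcomes. This is fair: the both-arm cases (17 or 14 against 20) are the more moderate illustration, and unequal loss is possible but not documented.
- **Removal may be rare.** The rule says subjects can be removed, not that they will be. The inclusion criteria ask for compliant patients able to complete the regimen, and the protocol provides weekly calls to oxygen-arm patients, counselling and home visits. These make large losses less likely; they do not say what happens when a removal occurs.
- **Outcomes may not be wholly lost, and nobody is excluded.** Images are taken at weeks 4, 8 and 12, groups are defined by randomisation, and Table 1 and the SF-36 text suggest follow-up of everyone. But earlier images do not give week-16 status, no rule says how to use them, and schedules written for participants do not settle the position of someone removed from the study.

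**Conclusion.** The concern holds and should be fixed. The plan contains a stated rule under which outcomes can be lost after randomisation for reasons related to healing, possibly unevenly by arm, and it does not say how those patients are followed or analysed. That is more than a missing detail, because the affected rates are the ones wanted for designing the larger trial.

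The direction and size of any bias are unknown. With assumed losses of 2 to 4 of 20 per arm, the next trial would be sized at 17 or 14 per arm instead of 20 if both arms lose non-healers, and at 12 to 37 in the one-arm extremes. There is no bias in the oxygen rate if those lost healed at the same rate as those kept. The 80% power claim is unaffected. Confidence is medium, because the text on universal follow-up is suggestive and removal may prove rare.

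**What to change.** - **Compliance:** replace removal from the study with wording under which noncompliance does not end outcome follow-up. Reconcile the term discontinued with At Home Treatments (whose list of reasons for ending treatment omits this rule), the Week 16 section and Adverse events, so that it is clear whether oxygen alone is meant. When oxygen stops is for the investigators to decide.
- **Week 16 / Follow-up:** apply the week-16 visit and imaging to every randomised patient unless consent is withdrawn, in line with Table 1 and the Quality of life section.
- **Statistical analysis:** make the primary analysis all randomised patients in their assigned group, with a stated rule for a missing outcome (for example, counted as not healed) and a sensitivity analysis under a different assumption. Say that the rule also covers any of the eleven subjects already enrolled who may have been removed; the documents do not say whether any were. Report removals by arm with reasons.

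**Cost.** Three wording changes, plus staff time and some home visits for the least compliant patients. The visits are already scheduled and paid for ($25, or $15 at home).

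Counting missing as not healed can lower the apparent effect. With 20 per arm and a one-sided Fisher test at 0.05, power falls from 83.7% to 74.1% or 61.9% if 10% or 20% of oxygen patients are so counted (50% read as 45% or 40%, SoC at 10%). If the same share is so counted in both arms (45% vs 9%, 40% vs 8%), it falls to 77.3% or 69.5%. The rule can also bias downward: two oxygen healers counted as not healed read 8/20 = 40%, which sizes the next trial at 32 per arm. That is why the sensitivity analysis is needed.

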### **Data Safety Monitoring:**

Data will be reviewed by the PI and study coordinator on an ongoing basis.

### **Adverse events:**

Chronic wounds represent a visible manifestation of a highly morbid disease state. As such, during the duration of this study, the natural history of these patients includes a significant risk of infection, limb loss, myocardial infarction, and death. Although expected, these events will be reportable to the IRB (if they meet reporting criteria), which will monitor these events for differences between the two groups. Wounds which are highly exudative (produce copious fluid) and may become macerated or new ulcers may form. These adverse events are all results of the disease state. The use of Topical Oxygen does require that the disposable device be affixed to the skin of the leg with a self-adhesive tape. Patients will be specifically monitored for

disturbed skin integrity at the fixation point. If this occurs, local wound care including skin protectants will be provided and future treatments will employ fixation at a different location, either proximal or distal. If the problem recurs or is of significant severity in the opinion of patient or treating physician treatment will be discontinued.

**Benefits:**

This pilot study will result in determining if TO may be an effective treatment modality for healing of open diabetic wounds.

Timely access to this modality will significantly benefit the Indiana population with diabetes that suffers from chronic wounds, a costly segment of beneficiaries in Indiana's Medicaid/Medicare and dual eligible program. These improved health outcomes may also result in cost savings to Indiana's Medicaid program. Regardless of the results of this study, the findings may provide insights into the care of this patient population, which will allow doctors to better treat patients in the future.

**Alternatives:**

Patients do not have to participate in this study to receive treatment for their ulcer. All of the treatments provided in this research study are available outside of this study. If they choose not to participate in this study they may seek these treatments from their doctor or the study investigators.

**Payment:**

Subjects will be compensated up to a total of \$125 for their study participation. Each subject will be paid \$25 for the completion of each study visit, for a maximum of 5 visits. Study visits that are completed at the subject's home will be compensated at \$15 per visit. Subjects will only be compensated for completed visits. Subjects will receive payment through a pre-paid debit card. All currency is in U.S. dollars and is considered taxable income.

**Device Description, Approval Status, References, Role of GWR Medical, Inc. in this study:**

Upon initial consideration of TO devices after the passage of the Medical Device Amendments in 1979, FDA initially proposed classification of such devices into Class II based on the evidence of safety and effectiveness submitted to the General and Plastic Surgery Device Classification Panel. However, in the interim between the release of the proposed and final device classification regulations, FDA reconsidered the evidence provided and decided to classify TO devices as Class III due to the lack of sufficient evidence demonstrating safety and effectiveness. Then in 2006, FDA issued a proposed rule to reclassify TO devices as Class II, based primarily on the data presented

in three, then recent, studies. The device is an FDA cleared Class II Device, and not an investigational device. This device is currently being used in many clinical care settings. The U.S. Department of Veterans Affairs and New York Medicaid reimburses TO Therapy that is being given as a SOC treatment using this device.

**See attached FDA document titled: Federal Register /Vol. 76, No. 79 /Monday, April 25, 2011 /Rules and Regulations.**

**Role of GWR Medical, Inc. for this study include the following:**

- Provide TO devices for free.
- Provide digital imaging software to capture wound images for wound measurements.
- **Data Management:**

Data will be collected via paper, phone interviews, direct data capture from measurement instrument and stored electronically in REDCap and xls files on Department Server. The storage location will be backed up manually every week. Other data sources include outside lab data, data from INPC will be stored in separate electronic files and merged with the primary data as needed. Quality assurance steps will include: 1) built-in range checks; 2) testing of database by study team prior to moving to production mode. The following quality control methods will be used: single entry with random checks of accuracy; and 2) extraction and cleaning of data that will be used for analysis every 6 months.

**Statistical Analysis Plan:**

**Sample size.** Although the main objective of this pilot trial is not to detect the significant difference between the two study groups, rather to provide preliminary data for the design of future trial, with sample size of n=40 (n=20 in each arm) could also provide at least 80% power to detect superiority of the TO+SoC treatment success rate (50%) vs. SoC (10%) based on a one-sided Fisher's Exact test at a significance level of 0.05.

## Statistical analysis.

Univariate analysis will be done using frequencies, mean (SD), median (IQR) to describe the patient cohort. Cumulative incidence of wound healing rates 16 weeks post treatment with 95% confidence interval around the risk estimate will be computed for the two groups (SoC and TO+SoC). Bivariate logistic regression will be used to report the odds of wound healing among those with TO+SoC compared to SoC only. Bivariate analysis to compare secondary outcomes between the groups will be done using Chi-square or Fisher's exact tests for categorical variables and t-tests or Mann-Whitney tests for continuous variables (e.g. QoL ratings from SF-36, costs).

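### The power claim rests on a one-sided Fisher's exact test, but wound healing is assigned only a logistic regression, with no estimator named and no rule for an arm in which nobody heals

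*Combined protocol and SAP*

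**What the plan says.** In the combined protocol and SAP, the sample-size paragraph (under Statistical Analysis Plan) claims at least 80% power for superiority of topical oxygen plus standard of care (TO+SoC, 50% success) over standard of care alone (SoC, 10%), with 20 per arm. The basis is a one-sided Fisher's "Exact test at a significance level of 0.05". The same sentence limits the weight of the claim: "the main objective of this pilot trial is not to detect the significant difference between the two study groups".

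The Statistical analysis section gives two things for wound healing:
- for each arm, "Cumulative incidence of wound healing rates 16 weeks post treatment with 95% confidence interval around the risk estimate";
- between the arms, "Bivariate logistic regression will be used to report the odds of wound healing among those with TO+SoC compared to SoC only".

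Fisher's test appears only in the sentence that follows: "Bivariate analysis to compare secondary outcomes between the groups will be done using Chi-square or" Fisher's exact tests, for categorical variables. For the wound-healing comparison the section states no sidedness, no significance level, no estimator (maximum likelihood, exact or penalised) and no rule for a zero cell.

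The outcome itself goes by different names. The sample-size paragraph speaks of treatment success and the analysis section of wound healing. Under Study Assessments and Procedures, "Wound healing rates will be determined from wound area measurement at baseline vs final visit using wound photography and Wound Matrix".

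**The concern.** The test that carries the power is not the analysis named for the outcome it was computed for. With 20 per arm and an expected SoC rate of 10%, an arm with no healed wounds is quite likely, and ordinary logistic regression then has no finite odds ratio. The failure falls almost entirely on results that strongly favour the new treatment. An analyst who follows the text literally could print a p-value near 1 beside a very clear difference, and would have to choose a remedy after seeing the data. What is at stake is the comparative odds ratio and the test attached to it, not the description of each arm.

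**Working it through.** **Inputs.** From the sample-size paragraph: n = 20 per arm, success rates 0.50 and 0.10, one-sided Fisher's exact test, alpha 0.05. Assumptions: treatment success is the same binary outcome as wound healing, all 40 patients are evaluable, and the regression is fitted by maximum likelihood.

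**1. The plan's own figure.** Sum Bin(a; 20, 0.50) × Bin(b; 20, 0.10) over all 21 × 21 tables with one-sided Fisher p ≤ 0.05. Power = 0.8375, or 83.7%. At least 80% is correct for the stated test.

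**2. How often there is no finite odds ratio.** The maximum-likelihood odds ratio a(20 − b) / [(20 − a)b] is finite and non-zero only if neither arm is at 0 or 20.
- P(SoC 0/20) = 0.9^20 = 0.1216. A count of 0 or 20 on TO+SoC adds 2 × 0.5^20 ≈ 0.000002. Total 12.2%.
- Other SoC rates p (assumed range), by (1 − p)^20: 35.8% at 5%, 3.9% at 15%, 1.2% at 20%.
- Fewer evaluable patients (assumed), SoC rate 10%: 15.0% with 18 per arm, 18.5% with 16.

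**3. Where these trials fall.** With SoC at 0/20, one-sided Fisher p is 0.053 for 4/20 on TO+SoC and 0.024 for 5/20, so 5 or more is significant. At a 50% rate that covers 99.4% of the SoC 0/20 trials: 0.1216 × 0.994 = 0.1209 of all trials.

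**4. Example, 10/20 against 0/20.**
- Fisher, one-sided: C(20,10) / C(40,10) = 184,756 / 847,660,528 = 0.0002.
- Wald: one standard fit failed to converge and stopped at a log odds ratio of about 26 with a standard error of about 101,000. z ≈ 0.0003, p about 1, and the 95% interval runs in effect from 0 to infinity.
- Likelihood ratio: 2 × {20 ln 0.5 − [10 ln 0.25 + 30 ln 0.75]} = 2 × (−13.86 + 22.49) = 17.26 on 1 df, two-sided p = 0.00003. The 95% profile lower limit for the odds ratio is 8.4; there is no upper limit.
- Firth: in a 2 × 2 table the estimate equals the odds ratio with 0.5 added to each cell, (10.5 × 20.5) / (10.5 × 0.5) = 41.0; 95% profile interval 4.5 to 5466.
- SoC proportion: 0/20, exact 95% interval 0 to 16.8%. It remains usable.

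**5. Power of the regression, same enumeration.** The plan gives no sidedness, so both are shown.

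| Test | One-sided 0.05 | Two-sided 0.05 |
|---|---|---|
| Fisher's exact | 83.7% | 74.2% |
| Logistic, Wald (non-finite fits counted as not significant) | 78.1% | 69.1% |
| Logistic, likelihood ratio | 91.2% | 83.8% |

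Given SoC 0/20, 99.98% of trials are significant by the two-sided likelihood-ratio test. Its power should be read with care: when both arms heal at 10%, that two-sided test rejects in 8.5% of trials against a nominal 5%. One-sided Fisher rejects in 0.8%.

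**The case against.** The two paragraphs can be read together: one gives a test, with its sidedness and level, and the other an effect measure, since the regression is there to report odds. On that reading the omission is a drafting gap and not a contradiction. This is fair, and it lowers the weight. It does not close the gap, because the analysis section places Fisher's test under secondary outcomes and nowhere names it for wound healing.

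A reader might infer that the comparison would be unusable in one trial in eight. The documents do not support that. They name neither Wald inference nor maximum likelihood, and even under maximum likelihood the likelihood-ratio test and the profile lower limit remain available. What is lost is the finite point estimate and the upper limit. An unbounded upper limit is largely a property of 0/20 data, and Firth's 5466 is hardly more informative.

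A reader might also infer that the power claim is wrong, or that logistic regression forfeits power. Neither follows. The claim is correct for its stated test, and only Wald testing falls below 80%.

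Finally, this is a pilot whose main aim is not to detect a difference, and the per-arm proportions with their intervals can still inform the next trial. That stands, and it sets the severity.

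**Conclusion.** The point holds as a minor fix. The plan names no test for wound healing in its analysis section, and the one between-arm method it does name has, under ordinary maximum likelihood, no finite odds ratio or upper limit in 12.2% of trials at the design rates. In those trials default Wald output would mislead.

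The 12.2% rests on maximum likelihood, 20 evaluable patients per arm and a true SoC rate of 10%, for which the documents give no source. It ranges from 35.8% at a 5% rate to 1.2% at 20%. Depending on which test the regression is taken to imply, power lies anywhere from 69.1% to 91.2%. That is ambiguity about the analysis, not a demonstrated loss.

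**What to change.** Add to the Statistical analysis section:

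> Wound healing will be compared between arms by the one-sided Fisher's exact test at 0.05 specified in the sample-size paragraph. The odds ratio and its 95% confidence interval will be estimated by Firth-penalised logistic regression with profile-likelihood limits.

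Keep the per-arm cumulative incidence with its 95% interval as planned. Sample size, visits and data collection do not change.

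Costs to accept:
- Firth shrinks the odds ratio. For 10/20 against 2/20 it gives (10.5 × 18.5) / (10.5 × 2.5) = 7.4 (95% interval 1.7 to 44.3), against (10 × 18) / (10 × 2) = 9.0 by maximum likelihood (Wald interval 1.6 to 49.4).
- With a zero cell the upper limit stays very wide.
- A one-sided 0.05 test and a two-sided 95% interval can disagree near the border. For 10/20 against 4/20 the Fisher test is significant but the Firth interval includes 1. This direction of disagreement occurs in 1.6% of trials at the design rates, and the reverse in 0.06%.

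Separately, the sponsor should reconcile treatment success, wound healing and the area-based healing rates, so that one binary outcome is fixed before analysis. That includes whether healing is judged at Week 16 or at any time up to it, because the final-visit section foresees recurrence: "Patients will be instructed to contact the study Physician should the ulcer recur". The wording above does not decide this.
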